4.7 Discontinuation of treatment

Treatment will continue until maximal duration of maintenance therapy is reached (as specified in Section 4.0, Treatment Duration), or the occurrence of any of the following events:

- Disease progression
- Adverse event(s) that, in the judgment of the Investigator/Medical Monitor, may cause severe or permanent harm or which rule out continuation of maintenance study drug.
- Graft failure
- Development of grade III-IV acute GVHD
- Development of severe chronic GVHD
- Suspected pregnancy
- Inability to start planned cycle of tagraxofusp within 56 days of intended start date of each cycle.
- Major violation of the study protocol (to include subject noncompliance with study medications or protocol-specified procedures) at the discretion of the PI

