6.0 Adverse Events and Reporting Requirements

An adverse event (AE) is the appearance or worsening of any undesirable sign, symptom, or medical condition occurring after starting the study drug even if the event is not considered to be related to study drug. Medical conditions/diseases present before starting study drug are only considered adverse events if they worsen after starting study drug. Abnormal laboratory values or test results constitute adverse events only if they induce clinical signs or symptoms, are considered clinically significant, or require therapy.

The investigator (or physician designee) is responsible for verifying and providing source documentation for all adverse events and assigning the attribution for all adverse events for subjects enrolled.

For the purpose of this study, the investigational component of the treatment plan is tagraxofusp (SL-401). Therefore, serious and unexpected adverse events occurring from the time of infusion of tagraxofusp up to 30 days of the last infusion of tagraxofusp, as defined below, will be reported according to MDACC policy and procedures below. The end of active treatment is the completion of the last infusion of tagraxofusp. Serious adverse events must be followed until clinical recovery and laboratory test have returned to baseline, progression of the event has stabilized, or there has been acceptable resolution of the event.

AEs will graded according to the NCI Common Terminology Criteria for Adverse Events (CTCAE) version 5.0. A copy of CTCAE version 5.0 can be downloaded from the CTEP website https://ctep.cancer.gov/protocolDevelopment/electronic_applications/ctc.htm#ctc_50

Grade – Severity of the adverse event. Grades were developed using the following guidelines:

- Grade 0 – No adverse event or within normal limits
- 1 – Mild adverse event
- 2 – Moderate adverse event
- 3 – Severe adverse event
- 4 – Life-threatening or disabling adverse event
- 5 – Fatal adverse event

Abnormal laboratory values not included in the CTCAE guidelines will be defined per protocol.

Time for AE Collection

Adverse events will be collected from the start of the study drug until 30 days after the last infusion of tagraxofusp.

Adverse Event Reporting

The Investigator or physician designee is responsible for verifying and providing source documentation for all adverse events, and assigning attribution for each event on all subjects enrolled on this study.

Data collection

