Collection of adverse events will reflect the onset and resolution date and maximum grade. Intermittent events should be labeled as such and followed until resolution. If a patient is taken off study while an event still ongoing, this will be followed until resolution unless another therapy is initiated. Pre-existing medical conditions will be recorded only if an exacerbation occurs during the active treatment period.

Patients will be registered in MD Anderson's Clinical Trial Management System, OnCore.

Adverse events and all protocol specific data will be entered into the electronic case report form (REDCap).

Events not to be considered adverse events in this study are those related to original disease or expected in the post-allogeneic transplant period.

Isolated changes in laboratory parameters such as electrolyte, magnesium and metabolic imbalances, uric acid changes, elevations of LDH and alkaline phosphatase will not be monitored.

Concomitant medications

Patients treated on this protocol will require supportive care treatment (concomitant medications). These medications are considered standard of care and have no scientific contribution to the protocol; therefore no data will be captured on various medications needed or their side effects. All antiviral therapy will be captured in the medical record.

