6.1 Serious Adverse Event (SAE) Reporting

An adverse event or suspected adverse reaction is considered "serious" if, in the view of either the investigator or the sponsor, it results in any of the following outcomes:

- Death
- A life-threatening adverse drug experience – any adverse experience that places the patient, in the view of the initial reporter, at immediate risk of death from the adverse experience as it occurred. It does not include an adverse experience that, had it occurred in a more severe form, might have caused death.
- Inpatient hospitalization or prolongation of existing hospitalization
- A persistent or significant incapacity or substantial disruption of the ability to conduct normal life functions.
- A congenital anomaly/birth defect.

Important medical events that may not result in death, be life-threatening, or require hospitalization may be considered a serious adverse drug experience when, based upon appropriate medical judgment, they may jeopardize the patient or subject and may require medical or surgical intervention to prevent one of the outcomes listed in this definition.

Examples of such medical events include allergic bronchospasm requiring intensive treatment in an emergency room or at home, blood dyscrasias or convulsions that do not result in inpatient hospitalization, or the development of drug dependency or drug abuse (21 CFR 312.32).

- Important medical events as defined above, may also be considered serious adverse events. Any important medical event can and should be reported as an SAE if deemed appropriate by the Principal Investigator or the IND Sponsor, IND Office.
- All events occurring during the conduct of a protocol and meeting the definition of a SAE must be reported to the IRB in accordance with the timeframes and procedures outlined in "The University of Texas M. D. Anderson Cancer Center Institutional Review Board Policy for Investigators on Reporting Serious Unanticipated Adverse Events for Drugs and Devices". Unless stated otherwise in the protocol, all SAEs, expected or unexpected, must be reported to the IND Office, regardless of attribution (within 5 working days of knowledge of the event).
- All life-threatening or fatal events, that are unexpected, and related to the study drug, must have a written report submitted within 24 hours (next working day) of knowledge of the event to the Safety Project Manager in the IND Office. -

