- OnCore, will be utilized for safety reporting to the IND Office and MDACC IRB.
- Serious adverse events will be captured from the time of the first protocol-specific intervention, until 30 days after the last dose of drug, unless the participant withdraws consent. Serious adverse events must be followed until clinical recovery is complete and laboratory tests have returned to baseline, progression of the event has stabilized, or there has been acceptable resolution of the event.
- Additionally, any serious adverse events that occur after the 30 day time period that are related to the study treatment must be reported to the IND Office. This may include the development of a secondary malignancy.

Reporting to FDA:

- Serious adverse events will be forwarded to FDA by the IND Sponsor (Safety Project Manager IND Office) according to 21 CFR 312.32. A copy of this form will be submitted to Stemline Therapeutics at the same time it is submitted to the IND Office.

It is the responsibility of the PI and the research team to ensure serious adverse events are reported according to the Code of Federal Regulations, Good Clinical Practices, the protocol guidelines, the sponsor's guidelines, and Institutional Review Board policy.

Recommended Adverse Event Recording Guidelines

Attribution	Grade 1	Grade 2	Grade 3	Grade 4	Grade 5
Unrelated	Phase I	Phase I	Phase I	Phase I	Phase I
			Phase II	Phase II	Phase II
				Phase III	Phase III
Unlikely	Phase I	Phase I	Phase I	Phase I	Phase I
			Phase II	Phase II	Phase II
				Phase III	Phase III
Possible	Phase I	Phase I	Phase I	Phase I	Phase I
	Phase II	Phase II	Phase II	Phase II	Phase II
		Phase III	Phase III	Phase III	Phase III
Probable	Phase I	Phase I	Phase I	Phase I	Phase I
	Phase II	Phase II	Phase II	Phase II	Phase II
		Phase III	Phase III	Phase III	Phase III
Definitive	Phase I	Phase I	Phase I	Phase I	Phase I
	Phase II	Phase II	Phase II	Phase II	Phase II
		Phase III	Phase III	Phase III	Phase III

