8.0 Statistical Considerations

Type of study: Open label, single-arm, single center, Phase 2 clinical trial

Number of patients planned: 20

Expected accrual rate: 5-10 patients/year

Toxicity monitoring

Continuous monitoring of toxicity will be performed in all 20 patients. The first 3 patients will be treated with 9 mcg/kg in first 4 cycles. From cycle 5 and beyond in the first 3 patients, the dose will be 12 ug/kg/day. All subsequent patients will be treated with 12 ug/kg/day. Unacceptable toxicities are defined as tagraxofusp-related toxicities which prevent initiation of Cycle 2 of therapy (Any adverse event ³ grade 3 that is both a) considered related to tagraxofusp, and b) does not resolve to \leq grade 2 after a maximum delay of 56-days). Assuming a prior beta distribution of (0.4, 1.6), corresponding to an unacceptable toxicity rate of 30%, treatment will terminate if the $Pr(dt > 0.20 | \text{data}) > 0.95$, where dt is the toxicity rate attributable to the tagraxofusp treatment. The decision rule for terminating for toxicity is presented in Table 4 and the software used for this Bayesian toxicity monitoring rule is Multc Lean version 2.1.0. The operating characteristics for this rule are presented in Table 5. The method used to produce the decision rule and operating characteristics was designed by Thall, Simon, and Estey ^{26, 27} and extended by Thall and Sung. ²⁸

Table 4 Stopping criteria

Total Patients Enrolled	Stopping Condition (# of patients experiencing unacceptable toxicities)
3-4	3-4
5-8	4-8
9-11	5-11
12-14	6-14
15-18	7-18
19	8-19
20	Patient enrollment ends

Table 5 Operating characteristics

True % of DLTs	Pr (stopping early)	Average # of patients treated
0.05	0.00	20
0.10	0.01	20
0.20	0.11	19
0.30	0.38	16
0.40	0.70	12
0.50	0.91	9

Analysis

Demographic and baseline characteristics will be summarized. Categorical measures will be summarized using frequencies and percentages while continuous variables will be summarized using mean, standard deviation, median, minimum, and maximum.

The primary endpoint of the study is the tolerability of tagraxofusp post-SCT, where tolerability is defined as receipt of at least 75% of planned tagraxofusp doses in at least 4 cycles of therapy. The following table shows the exact 95% confidence intervals for different percentages of patients, out of 20 patients, experiencing tolerability:

Patients experiencing tolerability		95% Exact
Number	Percentage	Confidence Interval
2	10%	1.2% - 31.7%

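### Section 6.0 removes transplant-expected events from the adverse events without keeping those possibly related to tagraxofusp, which contradicts its own definition

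*Combined protocol and SAP*

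**What the plan says.** Section 1.0 makes safety after auto-HCT or allo-HCT the primary objective. Four pieces of text then decide which events enter the safety data.

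- **Definition (Section 6.0, opening).** A new or worsening undesirable event after the start of drug is an adverse event "even if the event is not considered to be related to study drug".
- **Attribution (Section 6.0, Adverse Event Reporting).** The investigator verifies adverse events and is responsible for "assigning attribution for each event on all subjects enrolled on this study".
- **Exclusion (Section 6.0, Data collection).** "Events not to be considered adverse events in this study are those related to original disease or expected in the post-allogeneic transplant period". No list of expected events is given, and possible relation to tagraxofusp is not mentioned.
- **Recording table (end of Section 6.1).** Under "Recommended Adverse Event Recording Guidelines", the Phase II entries cover grades 1 to 5 when attribution is possible, probable or definitive, and grades 3 to 5 when it is unrelated or unlikely. Section 8.0 describes the trial as Phase 2, so these entries apply.

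Nothing says which text governs when they differ.

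**The concern.** The exclusion has two grounds. The first, relation to the original disease, is about cause. The second, being expected after allogeneic transplant, is about whether the event is a familiar one. An event can be familiar after allo-HCT and still be caused by the drug, and the sentence removes it either way.

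The overlap is realistic. Under Section 4.1 treatment starts between Day +45 and Day +180 after transplant, so events after the first dose arise in a post-transplant period. Section 2.3.2 reports fatigue in 49%, nausea in 46% and thrombocytopenia in 35% of tagraxofusp-treated patients. Section 3.2 exempts nausea and fatigue from the prior-toxicity exclusion, so patients may enter with them. Whether a later worsening is recorded would then turn on what each investigator regards as expected.

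At stake is the completeness of the adverse event record in a 20-patient, single-arm safety study. The transplant ground names only the allogeneic setting, so its comparability across the two transplant groups is also at stake.

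**Working it through.** No arithmetic applies. The check is to take an event that is expected after transplant, occurring in an allo-HCT patient after the start of drug, and apply each text to it.

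| Attribution and grade | 6.0 definition | 6.0 exclusion | 6.1 table, Phase II |
|---|---|---|---|
| At least possibly related, grades 1–5 | Adverse event | Not an adverse event | Record |
| Unrelated or unlikely, grades 3–5 | Adverse event | Not an adverse event | Record |
| Unrelated or unlikely, grades 1–2 | Adverse event | Not an adverse event | Not listed |

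1. **Row 1 is the gap.** The definition and the table both bring the event in, and the exclusion takes it out.
2. **Row 2 is a conflict of a different kind.** These are events judged not to be due to the drug. Recording them or not is a choice about workload, but the plan should make that choice once.
3. **Row 3 does no harm.** Neither the exclusion nor the table would put the event in the record.
4. **Auto-HCT patients.** The transplant ground does not reach them on its wording, so the same row 1 event is recorded after auto-HCT and can be left out after allo-HCT.
5. **Order of steps.** Section 6.0 attaches the attribution duty to adverse events. An event already ruled not to be one has no attribution step in that section, so the text does not ensure that relatedness is considered before the event is set aside.
6. **Serious events.** Section 6.1 begins its definition with "An adverse event or suspected adverse reaction is considered", which is wider than adverse events alone. It sends all SAEs to the IND Office whether or not they are expected and whatever their attribution, unless the protocol says otherwise. That proviso leaves a little doubt, but the exposure is mainly among non-serious events.
7. **Primary endpoint.** Section 8.0 defines tolerability by the share of planned doses received in at least 4 cycles. It is not computed from adverse event records.
8. **Table 4.** A counted toxicity is an event of at least grade 3 "that is both a) considered related to tagraxofusp", among toxicities "which prevent initiation of Cycle 2 of therapy", that stays unresolved through the maximum delay. Such an event has already been attributed to the drug. Section 4.4 requires a judgement on tagraxofusp-related non-hematological toxicity before the next cycle. Section 4.7 lists as a reason for discontinuation "Inability to start planned cycle of tagraxofusp within 56 days of intended start date of each cycle". Section 8.0 also requires toxicity summaries to the IND Office after the first 3 evaluable patients and every 2 to 3 thereafter, following Table 4. An event of this kind is hard to miss.

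**The case against.** The best defence is a narrower reading. The second ground stands next to one about cause, so the sentence may be meant to exclude only background transplant events and to leave suspected drug reactions in place. That may well be the intention, but the sentence speaks of what is expected, not of what transplant caused, and nothing else in the plan supplies the limit.

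The defence can also say that the Section 6.1 table is only recommended and covers all trial phases, so a study-specific exclusion may take precedence. That weakens the conflict with the table. It does not remove the conflict with the definition in Section 6.0, which is not a recommendation.

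Third, drug toxicity is watched in other ways: the cycle-start check in Section 4.4, the laboratory and vital-sign thresholds in Table 3, the SAE route and the summary reports. This stands as protection for patients and for the stopping rule. None of it requires a non-serious event to be entered in the adverse event data.

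A reader might infer that the exclusion undermines the stopping rule, since Section 8.0 uses the term adverse event and one uncounted case at a Table 4 boundary would turn a stop into a continuation. The second part is true by construction, because the table lists the smallest count that stops. It says nothing about how likely a miss is. The counted events are those least likely to be dismissed as background, so the documents do not support this stronger reading.

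**Conclusion.** The exclusion is wrong as written: it contradicts the definition in its own section and is inconsistent with the recommended Phase II recording. Taken literally, it lets possibly drug-related events in allo-HCT patients, mainly non-serious ones, go unrecorded, and allows the two transplant groups to be recorded differently.

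The size cannot be derived. The documents give neither the allo-HCT share of the 20 patients, nor a list of expected events, nor how often such events would be judged possibly related. The conclusion rests on the literal wording. If every investigator applied the narrower reading, no possibly drug-related event would be lost on the transplant ground. The matter should be corrected because safety is the primary objective, but it does not threaten the primary endpoint and is unlikely to affect Table 4.

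**What to change.** Reconcile the Section 6.0 definition, the Section 6.0 exclusion and the Section 6.1 table by adding after the exclusion:

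*This exclusion does not apply to any event considered at least possibly related to tagraxofusp; such events are recorded with grade and attribution in auto-HCT and allo-HCT patients alike, and those meeting the Section 8.0 definition count toward Table 4.*

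State separately whether the exclusion or the Section 6.1 table governs grade 3 to 5 events judged unrelated or unlikely. Recording all of them would add background transplant events, possibly over 24 or more cycles, and either answer is defensible if it is written down.

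The cost is one or two sentences and a somewhat longer adverse event listing. The change does not touch the sample size, the visits, the primary endpoint or the stopping boundaries. It is best made early, since events that were never recorded may be hard to recover.

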2.3.2 Safety data

The most common individual treatment emergent adverse events (TEAEs) reported to date with tagraxofusp, regardless of dose, were ALT increased (69 patients, 55%) and AST increased (68 patients; 54%); hypoalbuminemia (66 patients; 53%); fatigue (61 patients, 49%); nausea (58 patients; 46%); peripheral edema (55 patients; 44%); pyrexia (54 patients; 43%); thrombocytopenia (44 patients; 35%), and headache and hyperglycemia (each 38 patients; 30%). A summary of the most common (i.e.; incidence ≥10%) TEAEs reported among tagraxofusp -treated patients, regardless of dose, is presented in Table 2. See Version 4.0 of the SL-401 Investigators Brochure for additional safety information.

Table 2. Most Common (≥ 10%) Treatment-Emergent Adverse Events, Overall and by Indication/Study, by MedDRA Preferred Term (Safety Population)

MedDRA Preferred Term	Stemline-Sponsored Study				Total	
	Study 0114 (BPDCN)	Study 0114 (AML)		Study 0314		
		(N=47) n (%)	(N=49) n (%)	(N=14) n (%)		
At least 1 TEAE	47 (100.0)	49 (100.0)	14 (100.0)	15 (100.0)	125 (100.0)	
Alanine aminotransferase increased	30 (63.8)		30 (61.2)	6 (42.9)	3 (20.0)69 (55.2)	
Aspartate aminotransferase increased	28 (59.6)		33 (67.3)	5 (35.7)	2 (13.3)68 (54.4)	
Hypoalbuminemia	26 (55.3)		30 (61.2)	7 (50.0)	3 (20.0)66 (52.8)	
Fatigue	21 (44.7)		27 (55.1)	6 (42.9)	7 (46.7)61 (48.8)	
Nausea	21 (44.7)		26 (53.1)	6 (42.9)	5 (33.3)58 (46.4)	
Oedema peripheral	24 (51.1)		19 (38.8)	3 (21.4)	9 (60.0)55 (44.0)	

		Stemline-Sponsored Study			
	Study 0114 (BPDCN)	Study 0114 (AML)	Study 0214	Study 0314	Total
Pyrexia	21 (44.7)		22 (44.9)	5 (35.7)	6 (40.0)54 (43.2)
Thrombocytopenia	23 (48.9)		11 (22.4)	6 (42.9)	4 (26.7)44 (35.2)
Headache	12 (25.5)		16 (32.7)	4 (28.6)	6 (40.0)38 (30.4)
Hyperglyc1emia	17 (36.2)		17 (34.7)	3 (21.4)	1 (6.7)38 (30.4)
Chills	16 (34.0)		12 (24.5)	5 (35.7)	3 (20.0)36 (28.8)
Dyspnea	6 (12.8)		18 (36.7)	3 (21.4)	9 (60.0)36 (28.8)
Anemia	11 (23.4)		13 (26.5)	3 (21.4)	7 (46.7)34 (27.2)
Hypotension	13 (27.7)		16 (32.7)	2 (14.3)	3 (20.0)34 (27.2)
Decreased appetite	12 (25.5)		15 (30.6)	2 (14.3)	4 (26.7)33 (26.4)
Weight increased	18 (38.3)		11 (22.4)	3 (21.4)	1 (6.7)33 (26.4)
Vomiting	8 (17.0)		14 (28.6)	3 (21.4)	5 (33.3)30 (24.0)
Diarrhea	7 (14.9)		13 (26.5)	3 (21.4)	6 (40.0)29 (23.2)
Dizziness	8 (17.0)		12 (24.5)	3 (21.4)	6 (40.0)29 (23.2)
Back pain	12 (25.5)		10 (20.4)	2 (14.3)	4 (26.7)28 (22.4)
Constipation	11 (23.4)		10 (20.4)	2 (14.3)	4 (26.7)27 (21.6)

		Stemline-Sponsored Study			

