	Study 0114 (BPDCN)	Study 0114 (AML)	Study 0214	Study 0314	Total
Capillary leak syndrome	9 (19.1)	10 (20.4)		2 (14.3)	4 (26.7)25 (20.0)
Hypokalemia	10 (21.3)	11 (22.4)		1 (7.1)	3 (20.0)25 (20.0)
Febrile neutropenia	5 (10.6)	17 (34.7)		1 (7.1)	023 (18.4)
Insomnia	7 (14.9)	8 (16.3)		2 (14.3)	6 (40.0)23 (18.4)
Cough	3 (6.4)	13 (26.5)		2 (14.3)	4 (26.7)22 (17.6)
Hypocalcemia	11 (23.4)	8 (16.3)		1 (7.1)	2 (13.3)22 (17.6)
Tachycardia	7 (14.9)	10 (20.4)		2 (14.3)	2 (13.3)21 (16.8)
Pain in extremity	5 (10.6)	8 (16.3)		1 (7.1)	5 (33.3)19 (15.2)
Hyponatremia	9 (19.1)	7 (14.3)		1 (7.1)	1 (6.7)18 (14.4)
Neutropenia	8 (17.0)	7 (14.3)		2 (14.3)	1 (6.7)18 (14.4)
Anxiety	9 (19.1)	4 (8.2)		0	4 (26.7)17 (13.6)

Hypertension	10 (21.3)	5 (10.2)	0	2 (13.3)17 (13.6)
Epistaxis	3 (6.4)	11 (22.4)	1 (7.1)	1 (6.7)16 (12.8)
Blood alkaline phosphatase increased	5 (10.6)	9 (18.4)	1 (7.1)	015 (12.0)
Blood lactate dehydrogenase increased	5 (10.6)	8 (16.3)	2 (14.3)	015 (12.0)
Abdominal pain	4 (8.5)	5 (10.2)	2 (14.3)	3 (20.0)14 (11.2)
Blood creatinine increased	6 (12.8)	6 (12.2)	2 (14.3)	014 (11.2)
Hypoxia	3 (6.4)	6 (12.2)	1 (7.1)	3 (20.0)13 (10.4)
Myalgia	1 (2.1)	8 (16.3)	2 (14.3)	2 (13.3)13 (10.4)

In response to the initial case of Grade 5 CLS, which occurred in a patient with BPDCN treated at the 7 mcg/kg dose level early in the clinical program in Study SL-401-0114, all tagraxofusp protocols were amended to exclude patients with left ventricular ejection fraction (LVEF) below the institutional lower limit of normal, and specify that tagraxofusp infusions should be withheld for patients who have an increase in body weight during the dosing period or other potential early evidence of CLS. After the occurrence of Grade 4 CLS, additional precautions were implemented in all tagraxofusp protocols, including instructions that tagraxofusp dosing cease within a given cycle in the setting of substantial albumin reductions or Grade 3 transaminase elevations. The second Grade 5 case of CLS occurred in a patient with AML treated with tagraxofusp at the 16 mcg/kg dose level, in Study STML-401-0114, a dose level above the MTD determined in that study of 12 m/kg/day.

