5.0 Evaluation During Study

Every effort will be made to adhere to the schedule of events and all protocol requirements. Variations in schedule of events and other protocol requirements that do not affect the rights and safety of the patient will not be considered as deviations. Such variations may include laboratory assessments completed outside of schedule and occasional missed required research samples. Missed samples for correlative studies will not constitute protocol deviations.

Table of Evaluations

	Pre-treatment ²	Pre-Infusion	Cycles 1-6 ¹					Cycles 7-12			Cycles 13+	
			Day 1	Day 2	Day 3	Day 7	Day 15 ⁵	Day 1	Day 2	Day 15 ⁵	Day 1	Day 2
Physical exam	X ³		X ⁴			X	X	X ⁴			X ⁴	
Vital signs	X	X	X	X	X	X	X	X	X	X	X	X
Weight	X	X	X	X	X	X	X	X	X	X	X	X
Lab tests	X ⁶	X ⁷	X	X	X	X	X		X	X	X	X
Pregnancy test	X ⁸											
12-lead EKG	X	X ⁹	X									
ECHO, PFTs	X											
Bone Marrow aspiration/biopsy	X ¹⁰											
CT (chest, abdomen, pelvis)	X											
Lumbar puncture	X ¹¹											
AE, SAE Monitoring		X	X	X	X	X	X	X	X	X	X	X

1 Cycle 1: Administered as inpatient. While in the hospital, the observation post-dosing should continue, as clinically indicated, until it is clear that the patient doesn't have evidence/symptoms of capillary leak syndrome (e.g., no weight gain, edema, hypotension, or decrease in albumin) or hypersensitivity reaction. At discharge after Cycle 1: At least once/week for 2 weeks: Physical exam, vital signs, weight, AE and SAE monitoring, clinical lab tests: CBC w/diff; serum electrolytes and chemistry (including albumin), and coagulation parameters.

2 Pre-treatment evaluations: Within 30 days of enrollment unless otherwise specified.

3 Physical exam, pre-treatment: Include detailed skin examination (+/- skin biopsy, as clinically indicated).

4 Physical exam, Cycles 1-6, Cycles 7-12 and Cycle 13+ Day 1: Within 48 hours of tagraxofusinfusion.

5 Day 15: (+/-3 days).

6 Pre-treatment labs: CBC with differential, serum chemistries including electrolytes, renal function tests, coagulation parameters, albumin, and liver function tests, lactate dehydrogenase (LDH), uric acid HIV/Hepatitis B and/or C.

7 Pre-infusion labs: CBC with differential, serum electrolytes and chemistry (including albumin), renal function tests, and liver function tests, lactate dehydrogenase (LDH), uric acid and coagulation parameters.

8 Serum or urine pregnancy test for women of child bearing potential (WOCBP), within 14 days of starting treatment.

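### Section 6.0 drops listed isolated laboratory changes from monitoring with no grade limit and no definition of isolated, so their rates can be under-recorded

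*Combined protocol and SAP*

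**What the plan says.** Under Data collection, Section 6.0 says: "Isolated changes in laboratory parameters such as electrolyte, magnesium and metabolic imbalances, uric acid changes, elevations of LDH and alkaline phosphatase will not be monitored". No grade is mentioned, drug-related changes are not excepted, and *isolated* is not defined.

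Three other places bear on this.

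- The opening of Section 6.0 gives the general rule: "Abnormal laboratory values or test results constitute adverse events only if they induce clinical signs or symptoms, are considered clinically significant, or require therapy".
- The recording guideline table at the end of Section 6.1 shows Phase II in every grade column for possible, probable and definitive attribution, that is, from Grade 1.
- Section 5.0, footnote 7, has these drawn before infusion, besides the blood count: "serum electrolytes and chemistry (including albumin), renal function tests, and liver function tests, lactate dehydrogenase (LDH), uric acid and coagulation parameters".

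The analysis text of Section 8.0 covers baseline characteristics, tolerability, PFS and OS, and then the periodic summary reports. It specifies no tabulation of laboratory values.

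**The concern.** The primary objective in Section 1.0 is safety. Table 2 in Section 2.3.2 shows that several of the excluded laboratory changes are common with this drug. It has rows for "Blood alkaline phosphatase increased" and "Blood lactate dehydrogenase increased" as well as for low potassium, calcium and sodium. If *metabolic* is taken to include glucose, the text of the same section adds "headache and hyperglycemia (each 38 patients; 30"%).

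Most of these tests are drawn in any case. Under the exclusion, though, a change may never become an adverse event record, and the analysis section names no other place where it would be summarised. Two coordinators who each follow a different sentence of Section 6.0 could record the same patient differently. The trial could then report low rates for these terms without any way of telling whether the low rate reflects the drug or the recording rule.

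**Working it through.** **1. Set the instructions side by side.** Consider an isolated low potassium of Grade 3, judged possibly related.

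| Case | General rule, Section 6.0 | Exclusion, Section 6.0 | Guideline table, Section 6.1 |
|---|---|---|---|
| Treated with replacement | Adverse event | Not monitored | Recorded for Phase II |
| Untreated, no symptoms, not called clinically significant | Not an adverse event | Not monitored | Not reached, if the table applies only to events already classed as adverse events |

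In the first row the sentences give opposite answers, and nothing says which prevails. In the second row they agree, and the change goes unrecorded although its grade is severe. Section 6.0 also says that supportive-care drugs will not be captured as data (antivirals go in the medical record). Whether a value needed therapy therefore cannot be checked from the trial data.

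**2. Check which tests are drawn.** Footnote 7 names electrolytes, chemistry, liver function tests, LDH and uric acid. Alkaline phosphatase is covered only by implication, and magnesium is not named.

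**3. Reproduce the Table 2 rates.** The denominator is 47 + 49 + 14 + 15 = 125. Each total is the sum of the four study columns, and the rate is p = total / 125.

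**4. Project to the planned 20 patients.** Expected cases = 20 × p. Probability of at least one case = 1 − (1 − p)^20. The last column uses the BPDCN column alone, 20 × count / 47.

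| Term | Sum of columns | p | Expected in 20 | P(at least one) | Expected, BPDCN rate |
|---|---|---|---|---|---|
| Hypokalemia | 10+11+1+3 = 25 | 20.0% | 4.0 | 0.988 | 4.3 |
| Hypocalcemia | 11+8+1+2 = 22 | 17.6% | 3.5 | 0.979 | 4.7 |
| Hyponatremia | 9+7+1+1 = 18 | 14.4% | 2.9 | 0.955 | 3.8 |
| Alkaline phosphatase increased | 5+9+1+0 = 15 | 12.0% | 2.4 | 0.922 | 2.1 |
| LDH increased | 5+8+2+0 = 15 | 12.0% | 2.4 | 0.922 | 2.1 |
| Hyperglycemia, if *metabolic* | 17+17+3+1 = 38 | 30.4% | 6.1 | 0.999 | 7.2 |

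All six percentages match those printed.

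**5. Interpret the counts.** They are all-grade cases expected if the Table 2 rates carry over to patients after transplantation. At those rates they are the most that could go unrecorded. Table 2 does not say how many cases were isolated, untreated or severe, so the share actually lost cannot be computed.

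**6. Check the decision rules.** The primary endpoint in Section 8.0 is receipt of at least 75% of planned doses in at least 4 cycles, which does not use adverse event records. The stopping rule counts "Any adverse event ³ grade 3 that is both a) considered related to tagraxofusp" (the ³ stands for ≥) and that also fails to resolve to Grade 2 or lower after a delay of up to 56 days, so that Cycle 2 cannot start. No sample size, boundary or operating characteristic changes.

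**The case against.** The strongest reply is that the two sentences of Section 6.0 can be read together: *isolated* changes are simply those that cause no symptoms, are not clinically significant and need no therapy. That is a sensible reading, but the plan does not state it. It also still leaves untreated related changes unrecorded, with grade playing no explicit part.

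Several further points stand.

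- The guideline table is headed as a recommendation and sorts events by grade and attribution. It does not define which laboratory values are adverse events, so its tension with the exclusion is weaker than that of the general rule.
- The laboratory triggers in Table 3 are albumin, transaminases and creatinine. The exclusion names none of them, although *metabolic* could be stretched to cover albumin.
- Serious adverse events go to the IND Office whatever their attribution.
- Section 6.0 sends all protocol-specific data to the electronic case report form, so the values may well be retained. What is missing is a plan to summarise them.
- Section 8.0 plans no formal comparison with Table 2.

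A reader might infer that every such change of any grade will go unrecorded, so that reported rates will be near zero. That would require the exclusion to override the general rule, which no sentence says, and every Table 2 case to be isolated. A reader might also infer that severe laboratory toxicity can bypass the stopping rule. For that, a change would have to block Cycle 2 through the full delay and yet be neither treated nor judged clinically significant, which is remote.

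**Conclusion.** The point holds within limits. The exclusion is written without a grade limit, an exception for related changes or a definition of its key word. It is not reconciled with the general rule or the recording guideline, and no laboratory summary stands behind it. The rates of the listed laboratory terms can therefore be under-recorded in a trial whose primary objective is safety.

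At Table 2 rates the ceiling is about 2.4 to 4.0 patients per term out of 20, or 6.1 for hyperglycemia if that term is included. This assumes that pre-existing rates apply after transplantation; the BPDCN column alone gives 2.1 to 4.7, and 7.2 for hyperglycemia. The true loss lies between none and these figures, and the documents do not allow a closer estimate.

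The documents do not support the broader conclusion, which a reader might draw, that the safety profile as a whole will be understated. Transaminases, creatinine, clinical events and serious adverse events lie outside the exclusion. The primary endpoint is not directly affected, and any effect on the stopping rule is probably negligible. This is a change the sponsor should make, because the gain in safety data is specific and the cost is low.

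**What to change.** Replace the exclusion sentence with three provisions.

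1. Laboratory values already drawn under Section 5.0 are graded by CTCAE v5.0, and the worst grade per patient is tabulated against baseline. Add this table to the Section 8.0 analysis text.
2. An abnormality is recorded as an adverse event, with attribution, if it is Grade 3 or higher, if it meets the general rule at the start of Section 6.0, or if it leads to a withheld, delayed or omitted dose.
3. Only isolated Grade 1–2 changes with no clinical significance, symptoms, treatment or dosing action stay off the adverse event form. This also serves as the definition of *isolated*.

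Then align the general rule and the Section 6.1 guideline table with this wording. Defining *isolated* alone would remove the ambiguity, but it would not recover untreated changes; the tabulation does that.

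No new samples are needed and the sample size does not change. The cost is a modest amount of data export and adverse event entry, and a somewhat less favourable-looking safety table.
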